## 9.1 Summary table: research tissue and blood specimen collection

Research Sampling	Time point	Contents
Blood	Cycle 1 Day 1	1-9 mL Streck Tube 5- 10mL green top tubes*
	Every Cycle Day 1	5- 10mL green top tubes *
	Restaging Visits Only	1-9mL Streck Tube
	Off Treatment for PD	1-9mL Streck Tube 5- 10mL green top tubes*
	Time of PD, in patients who came off-study for a reason other than PD (Optional)	1-9mL Streck Tube 5- 10mL green top tubes*
Fresh Tissue	Pre-treatment (Optional) – within 7 days of starting therapy	5-7cores
	Progression**	5-7cores
Archival Tissue	Anytime	1 block or 20, 4 micron unstained slides

Stool Sample	Pre-treatment (within 28 days of starting therapy)	Home Stool Kit (DNA Genotek)
	Cycle 3 Day 1 (within 14 days prior)	
	Disease Progression	
	At the time of grade $\geq 2$ diarrhea (Optional)***	

\* EDTA (purple top) tubes or CPT tubes may be used interchangeably with green top tubes

\*\*Biopsy at the time of disease progression is optional for subjects on Arm A. Subjects on Arm B will be required to undergo a biopsy if they have accessible disease at the time of progression on Eribulin therapy, prior to initiating crossover treatment. Subjects on Arm B Crossover Therapy may choose to undergo an optional biopsy at the time of disease progression.

\*\*\* Collection at the time of grade  $\geq 2$  diarrhea is optional and should be discussed with the study PI.

## 9.2 Fresh Tissue Collection

### 9.2.1 Collection and handling of biopsy specimens

Biopsies are optional at baseline (within 7 days of starting therapy) and at the time of disease progression for subjects on Arm A and subjects on Arm B Crossover Therapy. There will be a required biopsy for subjects with accessible disease on Arm B who experience disease progression on Eribulin mesylate prior to initiating crossover therapy. Guidelines for biopsies from various metastatic sites can be found in Appendix C. Additional collection and processing instructions may be found in the separate laboratory manual.

Ideally five core biopsies will be obtained:

- Two cores should be placed in 10% neutral buffered formalin tube supplied by the study.
- One core should be placed in RNAlater
- Two cores should be placed in sterile DMEM

## 9.3 Procedures for obtaining blood and stool specimens for study

### 9.3.1 Blood Collection

Research blood collection is mandatory for all participants for flow cytometry and DNA isolation. The samples will be banked in the DF/HCC Clinical Trials Core Laboratory for these and future research purposes. These specimens will become the property of the DF/HCC.

Please refer to the separate laboratory manual for collection and processing instructions

### 9.3.2 Handling of Blood Specimens

All samples should be de-identified and labeled with the Participant initials, Participant Study ID number and date of collection and time point (e.g., “Baseline” or “Cycle 1” or “Progressive

Disease"). Please refer to the separate laboratory manual for collection and processing instructions.

- Green Top tubes:  
Five 10mL green top, purple top, or CPT tubes should be filled completely and should be processed within 3-4hrs of being drawn. Will be delivered or shipped, ambient overnight to [name]'s lab. Please contact the lab ahead of time by approximately one week to notify of upcoming specimen drop off.
- Streck tubes:  
Fill the Streck tube completely and immediately mix by gentle inversion 8 to 10 times. Inadequate or delayed mixing may result in accurate results.

Tube precautions:

- DO NOT FREEZE OR REFRIGERATE TUBES as this could result in cfDNA breakage. Blood collected in the Streck tube can be stored for 14 days between 6-37 degrees Celsius.
- Do not use tubes after expiration date.
- Fill the tube completely; overfilling or underfilling of tubes will result in an incorrect blood-to-additive ratio and may lead to incorrect analytical results.

### 9.3.3 Stool Collection

All stool samples will be collected by each patient at home using a home-based kit with a pre-paid mailer that provides nearly equivalent metagenomic and metatranscriptomic data to state-of-the-art fresh-frozen sample-collection protocol. Patients will be asked to provide samples at the following timepoints:

- Baseline
- After two cycles of therapy
- At the time of disease progression
- Optional collection at the time of grade  $\geq 2$  diarrhea

Most kits will be provided to the patients at their clinic visits. If the study team is unable to provide the kits to the patients in clinic, they may be mailed to patients by members of the study team. All kits will contain a questionnaire for patients to complete and return with their samples regarding timing and conditions surrounding their stool sample.

Please refer to the separate lab manual for collection and processing instructions.

Samples will be stored at the BWH/Harvard Cohorts Repository and will be shipped out to an external lab vendor, Microbiome Dx, who will perform the analysis of the samples.

### 9.4 Sites Performing Correlative Studies

DFCI Center for Immuno-Oncology  
DFCI Clinical Trials Core Laboratory

BWH/Harvard Cohorts Biorepository  
Microbiome Dx – External Lab Vendor

## **9.5 Blood, tissue and stool banking**

Any leftover blood, tissue, or stool will be banked in the lab of [name] or the DF/HCC Clinical Trials Core Laboratory, respectively, as per standard lab protocol, such that it can be used for additional or future analyses as needed.

## **9.6 Hypothesis for correlative objectives**

### **9.6.1 Hypotheses**

- We hypothesize that the immune marker profile in the peripheral blood will change over the course of eribulin mesylate +/- pembrolizumab therapy.
- We hypothesize that a larger increase in markers of immune activity in the peripheral blood will correlate with a better disease response as assessed on concurrent restaging scans, and in terms of best radiographic response at any time on trial.  
We hypothesize that an immune marker or composite of markers in the peripheral blood at baseline will correspond to TIL percentage in archival tumor tissue.
- We hypothesize that the immune activity associated with a breast tumor, as assessed both in tumor tissue and in circulating blood, will be less at the time of disease progression on therapy compared to the time of therapy initiation.
- We hypothesize that the structure and function of the gut microbiome differs among patients with breast cancer.
- We hypothesize that the structure and function of the gut microbiome before starting pembrolizumab and eribulin can be predictive of efficacy of this therapy, with a greater microbial diversity, estimated by Shannon index, being predictive of efficacy.
- We hypothesize that the structure and function of gut microbiome changes in response pembrolizumab-based therapy and can predict the likelihood of response to pembrolizumab.
- We hypothesize that the abundance and functional profile of specific gut bacteria is associated with response to pembrolizumab.

## **9.7 Planned assays for correlative objectives**

All of the below-mentioned analyses may be altered based on novel developments in the field of cancer immune profiling at the time of correlative science. Additional markers or alternative technologies (based on scientific developments and/or novel technologies) may also be used, to explore potential prognostic or predictive candidate markers/panels or markers related to treatment benefit and/or safety, to improve diagnostic tests, or to understand breast cancer biology.

### 9.7.1 Tumor infiltrating lymphocyte (TIL) percentage and determination of lymphocyte predominant breast cancer (LPBC)

Paraffinized, hematoxylin and eosin-stained slides taken from two tissue planes will be derived from each biopsy and will be reviewed by certified pathologists. The extent of lymphocytic infiltrate in tumor tissue will be assessed, and stromal TIL percentage will be determined. More detailed guidelines for the quantification of stromal TILs in breast cancer can be found in the recommendations from the International TILs Working Group 2014.

After assessment of the TIL percentage, the specimen may be categorized as lymphocyte predominant breast cancer (LPBC), defined as a tumor that contains >60% stromal lymphocytes, or non-LPBC.

### 9.7.2 Immunohistochemistry

Tissue will be collected and fixed by 10% neutral buffered formalin overnight, dehydrated, and paraffin embedded. Four micrometer-thick sections will be cut. The paraffin blocks and unstained slides will be stored at room temperature. All immunohistochemical staining will be performed in the Center for Immuno-Oncology Pathology Core at Dana-Farber/Harvard Cancer Center (DF/HCC) Specialized Histopathology Core.

Formalin fixed-paraffin embedded (FFPE) tumor slides will be prepared and H&E stained for assessment of TIL in pre- and post-treatment tumor samples. To identify subsets of different immune populations (effector/memory CD8 cells, T regulatory cells, dendritic cells, tumor associated macrophages, and Tie-2 expressing monocytes (TEM)), immunohistochemical (IHC) staining will be performed on FFPE tumor slices using some or all of the following antibodies:  
Core set: CD8, PD-1, PD-L1, PD-L2  
Others: CD3, CD4, CD25, FoxP3, Indoleamine 2,3 deoxygenase-1 (IDO1), CD11c, CD83, CD86, CD56, CD14, CD16, Tie2 (See also Appendix E)

Chen et al describe a semi-quantitative scoring method, which is in accordance with typical biomarker scoring in anatomic and surgical pathology. Briefly, staining is scored according to intensity (0=no staining, 1=weak staining, 2=moderate staining, 3=strong staining), staining pattern (M=predominantly cell membrane; C=predominantly cell cytoplasm), and the percentage of cells showing positive staining (0-100%). The semi-quantitative scoring is performed for: 1) the neoplastic tumor cells and 2) the non-neoplastic infiltrating immune cells. Significant discordant results have been rare during case evaluations.

Further details of the immunohistochemical assay and assessment are described in the lab manual for this protocol.

It should be noted that the above staining protocols are based on standard methods used at the time of protocol writing. It is possible that at the time protein expression assays are conducted, novel and improved methods for staining will exist. In this case, we plan to use the best available, best validated experimental method available at the time.

### 9.7.3 Flow cytometry, genomic analysis of biopsy tissue

TILs will be isolated from the biopsy specimen and assessed by surface staining as described in the lab manual for this protocol.

Messenger RNA (mRNA) expression within tumor biopsy specimens will be assessed using the most current and informative methodologies at the time that correlative science is performed on all specimens. NanoString signatures and comprehensive RNA sequencing may be used. Potential genes of interest, based on prior immune profiling of breast tumors, include CXCL9, CCL5, CD8ACD80, CXCL13, IGKC, CD21, IDO1, PD-1, PD-L1, PD-L2, CTLA4, and FOXP3. Additional DNA analysis, for example to assess mutational load and neoantigen burden, may also be performed.

### 9.7.4 Analysis of PBMCs

PBMCs will be generated as described in the lab manual for this protocol, and used to assess immune cell populations by flow cytometry.

### 9.7.5 Analysis of cell-free DNA

Blood will be collected at baseline, restaging visits and at time of progression for evaluation of cell-free DNA (cfDNA). The cfDNA will be banked in the DF/HCC Clinical Trials Core laboratory for future research purposes. The banked samples will be used to analyze DNA, RNA and protein in future studies.

### 9.7.6 Analysis of 16S rRNA gene sequencing

Microbial DNA is extracted using the Mag-Bind Universal Pathogen DNA Kit (Omega Bio-Tek). Briefly, 250 mg of the specimen is transferred to a deep-well plate for bead beating followed by DNA precipitation and purification following the manufacturer's instructions. Finally, DNA is eluted in 100 uls of Elution Buffer and stored at -80°C until further use. 16S sequencing libraries are generated by amplifying the v3-v4 hypervariable regions of the 16S gene in a polymerase chain reaction using primers F341 and R785. Resulting amplicons are tagged with unique molecular barcodes that are later used to demultiplex sequencing reads into individual sample buckets. Libraries are loaded on a MiSeq flowcell and sequenced following Illumina's loading instructions. Sequence data are retrieved from the instrument by converting base call format files into fastq files for data processing purposes.

MicrobiomeDX uses BacProTM, a proprietary algorithm, to inspect and validate sequencing files by employing demultiplexing, trimming, merging, and quality filtering steps. Paired sequencing reads are merged using an overlap of 25 bp allowing for 10 base mismatches. Merged sequences are dereplicated and clustered in a de-novo fashion using VSEARCH, while filtering out sequence chimeras and singletons. Representative sequences from each cluster are mapped against the SILVA database at 99% sequence identity to obtain accurate taxonomic classifications and relative abundances. In parallel, feature tables are constructed to derive alpha diversity indices, and distance matrices are built to derive beta diversity indices. The BacProTM

pipeline generates a comprehensive report that includes alpha diversity scores describing community richness and evenness, taxonomic composition with relative abundances, and beta diversity metrics to determine the in-between sample differences based on the bacterial communities identified.

#### 9.7.7 Shotgun sequencing and metabolic pathway reconstruction of stool samples

Stool samples from patients included in the trial 2 will be subjected to whole genome shotgun sequencing. Libraries will be constructed with Illumina barcodes from the TruSeq DNA Sample Prep kit (Illumina) and reagents from KAPA Library Preparation kit (Kapa Biosystems), and then sequenced on an Illumina MiSeq platform using 2\_250 nucleotide paired-end sequencing, according to the manufacturer's instructions. Sequencing reads will be converted into relative abundances of microbial metabolic modules using HUMAnN35, the Human Microbiome Project metabolic reconstruction pipeline and mapped to the KEGG36. Relative species abundances will be calculated by the MetaPhlAn pipeline.

## 10. STUDY CALENDAR

Consent may be obtained **28 days** prior to the start of protocol therapy. Baseline evaluations are to be conducted within **21 days** prior to start of protocol therapy (unless otherwise specified). If these screening assessments occur within 3 days before start of study treatment, they do not need to be repeated on Cycle 1 Day 1. Scans must be done within **28 days** prior to the start of protocol therapy.

As detailed in the Study Calendar, a negative pregnancy test in women of child-bearing potential (as defined in the eligibility criteria) must be documented within **7 days** prior to the start of protocol therapy.

If participants agree to a baseline tumor biopsy, this biopsy should be obtained within **7 days** before starting protocol therapy.

In the event that the participant's condition is deteriorating, laboratory evaluations should be repeated within 48 hours prior to initiation of the next cycle of therapy.

Assessments must be performed prior to administration of any study agent. Study assessments and agents should be administered within  $\pm$  3 days of the protocol-specified date, unless otherwise noted.

Day 8 assessments may be performed at DFCI Milford, as needed; however, due to correlative requirements, the Day 1 visits, scans, and/or biopsies may not occur at this location.

	Screening	C1		C2		C3		Cycle 4 and subsequent cycles		Crossover a	Off-Treatment m	Follow-Up
		D1	D8 s	D1	D8 s	D1	D8 s	D1	D8 s			
Arm A- Drug administration												
Pembrolizumab		X		X		X		X				
Eribulin mesylate		X	X	X	X	X	X	X	X			
Arm B- Drug administration												
Eribulin mesylate		X	X	X	X	X	X	X	X			
Pembrolizumab										X		
Informed consent	X											
Demographics	X											
Medical history	X									X		
Physical exam	X	X		X		X		X		X	X	
Vital signs	X	X	X	X	X	X	X	X	X	X	X	
Weight	X	X		X		X		X		X	X	
Performance status	X	X		X		X		X		X	X	
Concurrent medications	X	X-----X										
Adverse event evaluation		X-----X										
Hematology panel b	X	X	X	X	X	X	X	X	X	X	X	
Chemistry panel c	X	X	X	X	X	X	X	X	X	X	X	
Cortisol l	X			X		X		X				
TSH d	X			X				X		X		
Coagulation panel (PT/PTT)	X											
Pregnancy test e	X									X		
EKG	X									X		
Tumor Assessments f, h	X						X g					X i
Tumor biopsy	X j									X k	X k	
Archival tumor samples l	X											
Research Blood Collection		X		X		X		X		X	X n	X o
Research Stool Collection q	X					X					X	
Stool Questionnaire r	X					X					X	
Survival												X p

1 cycle = 21 Days

a. Participants on Arm B crossing over to Pembrolizumab monotherapy must meet the criteria provided in Section 3.4 and 3.5 to begin therapy with pembrolizumab.

b. Hematology to include: CBCA

c. Chemistries to include: Chloride, potassium, sodium, BUN, serum creatinine, phosphorus, calcium, albumin, total protein, alkaline phosphatase, ALT, AST, total bilirubin (NOTE: the frequency of checking magnesium levels is left up to the treating provider)

- d. TSH collected at screening, C2D1, and every other cycle for participants receiving pembrolizumab. TSH is required at time of crossover.
- e. In female participants of child-bearing potential (as defined in the eligibility criteria), a urine or serum pregnancy test must be performed within 7 days prior to the first dose of study medication. If the urine test is positive or cannot be confirmed as negative, then a serum test is required. For female participants of child-bearing potential crossing over, a negative pregnancy test is also required within 7 days of starting crossover therapy.
- f. Baseline tumor assessments must be done within 28 days prior to the start of therapy. Tumor assessments will be performed every 3 cycles (9 weeks) for the first 18 cycles (1 year). If after Cycle 18 scans (1 year), a participant has SD or better by RECIST the frequency of assessments may be reduced to every 4 cycles (12 weeks). If treatment is delayed, scans should continue to align with cycles of treatment, rather than weeks on treatment. Effort should be made to use the same type of imaging to assess measurable lesions at baseline and in follow-up. Confirmatory scans 4 weeks after documented response should be obtained
- g. For any subject who showed first radiologic evidence of progressive disease (PD) by RECIST 1.1 (see Section 11.1.4) and is deemed clinically stable (see section 5.6), it is at the discretion of the investigator to continue treating the subject until progression is confirmed at least 4 weeks from the date of the first radiologic evidence of PD. If progression is confirmed, the subject will be discontinued from study treatment. Otherwise, the subject will continue treatment and radiographic scans. Any subject who had initial radiologic progression and is deemed clinically unstable should be discontinued from both study drugs and no subsequent scan for confirmation is required.
- h. Tumor assessments should continue as scheduled for participants on Arm B who crossover to receive pembrolizumab.
- i. During follow-up of patients who went off study for reasons other than PD, tumor assessments should continue every 9 to 12 weeks from the date of the last assessment until progressive disease is documented
- j. Optional biopsy should be obtained within 7 days before starting protocol therapy. See Section 9, appendices, and lab manual for biopsy handling and processing instructions.
- k. Optional tumor biopsy should be offered only in patients who go off study for progressive disease. See Section 9, appendices, and lab manual for biopsy handling and processing instructions. For patients randomized for the eribulin mesylate arm who wish to cross over to pembrolizumab arm, a biopsy at progression is mandatory for those whose disease is amenable for biopsy.
- l. 1 block or 20 unstained slides should be collected. If archival tissue is not available, patients with safely accessible disease should have a baseline biopsy.
- m. Off treatment visit is to occur within 30 days of final administration of study treatment. End of treatment assessments do not have to be repeated if the same assessments were performed within 7 days prior to the visit.
- n. Research blood should only be collected on patients who come off treatment for progressive disease.
- o. Optional blood collection for immune cells/cfDNA may be offered to patients who develop progressive disease during follow-up.
- p. Survival status should be collected annually, either by review of the medical record or by phone call (see Section 5.8).
- q. Baseline stool collection should be obtained within 28 days before starting protocol therapy. The C3D1 stool collection should be performed as close to C3D1 as possible, but may be collected up to 14 days prior. A sample will additionally be collected at the time of disease progression. An optional stool sample may be collected at the time of grade  $\geq 2$  diarrhea after discussion with the PI. Stool collections will not occur on Pembrolizumab Crossover therapy for patients randomized to Arm B. As these collections are for exploratory correlative purposes, failure to provide a sample at these timepoints will not constitute a protocol violation. See section 9 and/or lab manual for stool collection and processing instructions.
- r. Each stool collection kit will contain a questionnaire for the patients to complete regarding the conditions surrounding their collection. These will be a part of the kit and are not to be administered in clinic. Failure to complete these questionnaires are the required or optional timepoints will not constitute a protocol violation.
- s. D8 assessments may occur at DFCI Milford, as needed. Additionally, if a subject is on Arm A and discontinues Eribulin, D8 visits will not be required. D8 visits are also not required when Arm B subjects are receiving Crossover Pembrolizumab monotherapy.
- t. For Arm A subjects, Cortisol blood draws will be required at baseline and every D1. For Arm B subjects, Cortisol blood draws will be drawn at baseline, as treatment arm is likely unknown, and then not again until all D1s of Crossover treatment. This will not be required when on Eribulin alone.

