### **5. TREATMENT PLAN**

#### **5.1 Treatment Regimen**

This is a phase 2 study of treatment with eribulin mesylate +/- pembrolizumab, in metastatic HR-positive breast cancer. Eighty-eight participants will be randomized (1:1) to eribulin mesylate with pembrolizumab (Arm A) or eribulin mesylate (Arm B). Participants randomized to eribulin mesylate monotherapy will have the option to receive pembrolizumab monotherapy at time of progression but they must meet the criteria in section 5.2.3 and begin treatment within 2 months of progression to crossover. Eribulin mesylate will be administered on days 1 and 8 of each 21 day cycle. Pembrolizumab will be administered on day 1 of each 21 day cycle. If treatment is delayed, all protocol required assessments will be delayed accordingly.

Treatment will be administered on an outpatient basis. Reported adverse events and potential risks are described in Section 7. Appropriate dose modifications are described in Section 6. Details of the regimen are described in Table 1/2. No investigational or commercial agents other than those described below may be administered with the intent to treat the participant's malignancy.

Treatment regimen is described in Table 1 (Arm A) and in Table 2 (Arm B).

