## **6. DOSING DELAYS/DOSE MODIFICATIONS**

Dose delays and modifications will be made as indicated in the following section. The descriptions and grading scales found in the revised NCI Common Terminology Criteria for Adverse Events (CTCAE) version 4.0 will be utilized for dose delays and dose modifications. A copy of the CTCAE version 4.0 can be downloaded from the CTEP website [http://ctep.cancer.gov/protocolDevelopment/electronic\\_applications/ctc.htm](http://ctep.cancer.gov/protocolDevelopment/electronic_applications/ctc.htm).

Dosing interruptions are permitted in the case of medical / surgical events or logistical reasons not related to study therapy (e.g., elective surgery, unrelated medical events, patient vacation, and/or holidays). Subjects should be placed back on study therapy within 3 weeks of the scheduled interruption, unless otherwise discussed with the Sponsor. The reason for interruption should be documented in the patient's study record.

If there are dosing delays for any reason, all study assessments are to be delayed in the same fashion, such that that scans and other assessments occur in conjunction with cycles of treatment.

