**Eribulin mesylate doses may be delayed and/or reduced. No re-escalation will be allowed.**  
**Pembrolizumab may be delayed as a result of toxicities but there are no dose reductions allowed.**

**For toxicities in this Section, which are attributable to pembrolizumab alone, only pembrolizumab should be held as directed. It is permissible to continue eribulin mesylate despite discontinuation of pembrolizumab in these select cases. This will be left at physician discretion.**

**For toxicities in this Section, which are attributable to eribulin mesylate alone, it is permissible to continue pembrolizumab and is left to the treating investigator's discretion. If a decision to stop indefinitely eribulin mesylate is made, it is permissible to continue pembrolizumab despite discontinuation of eribulin mesylate in these select cases. This will be left at physician discretion.**

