## 6.2 Management of toxicities attributable to Eribulin mesylate

Subjects should be carefully monitored for toxicity. If a treatment delay is required for eribulin mesylate toxicity, treatment with pembrolizumab is allowed. If toxicities recur, the dose of eribulin mesylate should be reduced. Once reduced, the dose of eribulin mesylate will not be re-escalated.

Dose adjustment recommendations for eribulin mesylate are shown in Tables 6 and delays are discussed below in Table 7.

If treatment with eribulin mesylate is withheld permanently, participants are allowed to continue to receive pembrolizumab therapy.

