Peripheral neuropathy	Grade 2	For intolerable (as determined by physician and patient) grade 2, decrease eribulin mesylate by one dose level.
	Grade 3	Hold eribulin mesylate until recovery to grade $\leq 2$ then reduce by 1 dose level.
	Grade 4	Permanently discontinue eribulin mesylate
Non-hematologic toxicity	Grade 3, first occurrence	Hold eribulin mesylate until recovery to grade $\leq 2$ . Maximize supportive care measures. If symptom recovery occurs within 1 week, then eribulin mesylate may be resumed at the same dose if deemed appropriate by the investigator, otherwise, reduce by 1 dose level.
	Grade 3, despite maximal supportive measures	Hold eribulin mesylate until recovery to grade $\leq 2$ then reduce by 1 dose level.
	Grade 4	Hold eribulin mesylate until recovery to grade $\leq 2$ then reduce by 1 dose level.
ANC = absolute neutrophil count		

 
Toxicities graded in accordance with National Cancer Institute Common Toxicity Criteria for AEs, version 4.0
 
Discontinuation should be considered if a dose reduction to <math><0.7 \text{ mg/m}^2</math> is required.
 
A minimum of 6 days between D1 and D8 of eribulin mesylate administration will be required and a minimum of 10 days between D8 and D22 (i.e. D1 of next cycle) will be required.
 
If a patient does not meet criteria to receive Day 8 of eribulin mesylate, the investigator may decide to make up the dose on Day 15 of the cycle. If the Day 15 dose is given, the next cycle should not be initiated until 2 weeks later. If the Day 15 dose is held again, the next cycle may initiate the following week.
 
Once a dose is reduced, it should not be re-escalated.
 
Treatment with eribulin mesylate will be discontinued if participants require a delay greater than 3 weeks.
 
Treatment with pembrolizumab is allowed to continue if eribulin mesylate is discontinued.
 
		

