## 11. MEASUREMENT OF EFFECT

## 11.1 Antitumor Effect – Solid Tumors

Response and progression will be evaluated in this study using the new international criteria proposed by the Response Evaluation Criteria in Solid Tumors (RECIST) guideline (version 1.1) [Eur J Ca 45:228-247, 2009]. Changes in the largest diameter (unidimensional measurement) of the tumor lesions and the shortest diameter in the case of malignant lymph nodes are used in the RECIST criteria.

Pembrolizumab, like other immunotherapeutic agents, may produce antitumor effects by potentiating endogenous cancer-specific immune responses. The response patterns seen with such an approach may extend beyond the typical time course of image responses seen with cytotoxic agents, and can manifest as a clinical response after an initial increase in tumor burden or even the appearance of new lesions.

For any subject who showed first radiologic evidence of progressive disease (PD) by RECIST 1.1 (see Section 11.1) and is deemed clinically stable, it is at the discretion of the investigator to continue treating the subject until progression is confirmed at the next scheduled restaging (or with a confirmatory completed at least 4 weeks from the initial date of PD). If progression is not confirmed on the subsequent scan, the subject should continue to receive treatment and have radiographic scans performed according to the study calendar [approximately every 3 cycles (9 weeks) for the first 12 months and then every 4 cycles (12 weeks)]. If radiologic progression is confirmed, then the subject should be discontinued from all study treatment. If the treating investigator feels that the participant is clinically stable, demonstrates improved condition, or is clearly continuing to benefit from the treatment; the PI may approve the participant to continue to receive study treatment. In all participants, the date of progression will be documented as the first date progression was observed.

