### **13.4 Analysis of Primary Endpoints**

The primary analysis of the study will be the comparison of PFS per RECIST 1.1 between Arm A and Arm B using logrank test and group sequential methods to control the overall one-sided Type I error rate at 0.1.

The null and alternative hypotheses are defined using the hazard ratio (HR) of the Arm A to Arm B as:

$$\begin{aligned} H_0: & \text{ HR} \leq 1 \\ H_1: & \text{ HR} > 1 \end{aligned}$$

All inferences will be conducted in the intent-to-treat manner, and the survival function will be summarized using the Kaplan-Meier methods according to randomized treatment assignment. Final analysis will be performed after 70 PFS events are observed or at least 12 months after the last patient is enrolled on study, whichever occurs first.

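### Scans for the primary PFS endpoint slip with every dosing delay, so recorded progression dates can differ between arms if delays differ

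*Combined protocol and SAP*

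**What the plan says.** The calendar schedules tumour assessments every 3 cycles (9 weeks) for 18 cycles, after which they may move to every 4 cycles (12 weeks). Footnote f adds: "If treatment is delayed, scans should continue to align with cycles of treatment, rather than weeks on treatment". Section 5.1 has the same rule: "If treatment is delayed, all protocol required assessments will be delayed accordingly". Section 6 widens it: "If there are dosing delays for any reason, all study assessments are to be delayed in the same fashion", and names scans explicitly.

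Section 13.1 defines PFS from randomization, with censoring at the last disease evaluation. Section 11.1 fixes the event date: "In all participants, the date of progression will be documented as the first date progression was observed". The primary analysis in Section 13.4 is "the comparison of PFS per RECIST 1.1 between Arm A and Arm B using logrank test", at one-sided 0.1.

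The hold rules differ by arm because the drugs do. For toxicity attributed to pembrolizumab alone, Section 6 directs that "only pembrolizumab should be held as directed", and eribulin may continue. Section 6.2 says: "If a treatment delay is required for eribulin mesylate toxicity, treatment with pembrolizumab is allowed". The notes to Table 7 add: "Treatment with pembrolizumab is allowed to continue if eribulin mesylate is discontinued". Arm B has no second drug before crossover.

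Off treatment, before progression, the intervals are in calendar weeks but do not agree. Section 5.8 gives 9 weeks up to week 27 and 12 weeks beyond week 54, with nothing between. Footnote i gives 9 to 12 weeks without saying when each applies.

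**The concern.** A progression found on imaging gets the date of the scan that finds it. If that scan moves with dosing, the recorded date depends on something that happens after randomization and may be related to treatment. An arm scanned later appears to have longer PFS with no true difference. The logrank test takes the dates as given. Section 13 has no interval-censored analysis, no sensitivity analysis for scan timing and no rule for late scans.

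The arms have different routes to delay, and these pull in opposite directions. Pembrolizumab holds exist only in Arm A and could make its scans later. Continuing pembrolizumab while eribulin is held could keep Arm A on schedule while Arm B slips. If eribulin is stopped before progression, an Arm B patient moves to the looser off-treatment schedule, while an Arm A patient may stay on cycle-based scans. The protocol does not say whether holding one of two drugs delays the cycle for scanning purposes.

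At stake are the type I error if Arm A is scanned later and the power if Arm B is.

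**Working it through.** **Inputs from the documents.** 44 patients per arm; median PFS 4.1 v 7.1 months (HR 0.58); 70 events; one-sided alpha 0.1; stated power 83%; 18 months' accrual plus 6 months' follow-up; 5% lost at one year (all Section 13.2). Scan intervals are from footnote f, and the ±3-day window is from Section 10.

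**The plan's own figure.**
- Schoenfeld: Φ(√70/2 × |ln 0.58| − 1.2816) = Φ(2.279 − 1.282) = 84.1%.
- Freedman: Φ(√70 × 0.42/1.58 − 1.2816) = Φ(2.224 − 1.282) = 82.7%.
- Schoenfeld with the futility rule (Z < 0 at 35 events): 82.6%, or 83.0% with HR = 4.1/7.1.
- Expected events at 24 months: 69.9, against 70 stated.

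The design reproduces.

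**Simulation 1.** Exponential PFS; scans every 9 weeks for 54 weeks, then every 12; each interval lengthened by a Poisson number of weeks capped at 3; scan date ±3 days; 10% of events are deaths dated exactly; censoring at the last scan; logrank at 70 events; no futility stop. The delay model, the death share and all differences between arms are assumptions.

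| Mean delay per interval, A / B (weeks) | Type I error | Power |
|---|---|---|
| 0 / 0 | 0.096 | 0.830 |
| 0.5 / 0.5 | 0.106 | 0.822 |
| 1 / 1 | 0.100 | – |
| 0.6 / 0.5 | 0.110 | – |
| 0.75 / 0.5 | 0.130 | 0.859* |
| 1 / 0.5 | 0.147 | – |
| 1.5 / 0.5 | 0.165 | 0.876* |
| 0.5 / 0.75 | 0.083* | 0.804 |
| 0.5 / 1 | 0.065* | 0.787 |
| 0.5 / 1.5 | 0.055* | 0.773 |
| 0.5 / 0 | 0.187 | – |
| 1 / 0 | 0.180 | – |

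There were 10,000 trials per type I figure (standard error 0.003) and 6,000 per power figure (0.005); starred entries come from 5,000 trials. The average apparent HR under the null runs from 0.99 (0.6 / 0.5) to 0.91 (0.5 / 0). With 20% deaths, a ±7-day window or both, 1 / 0.5 gives 0.135–0.143 and 0.5 / 0 gives 0.156–0.168.

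**Simulation 2, a different delay model.** A share of 9-week intervals is lengthened by 0 to 3 weeks (uniform); all events are dated by scan; 8,000 trials each.

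| Share of intervals delayed, A / B | Type I error | Power |
|---|---|---|
| none | 0.102 | 0.836 |
| 50% / 50% | 0.106 | 0.838 |
| 60% / 40% | 0.129 | 0.849 |
| 50% / 25% | 0.138 | 0.859 |
| 50% / 0 | 0.189 | 0.892 |
| 40% / 60% | 0.078 | 0.802 |
| 25% / 50% | 0.077 | 0.793 |
| 0 / 50% | 0.047 | 0.762 |

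With 20% of events as deaths dated exactly, the type I range narrows to 0.060–0.160.

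**Using the protocol's one delay figure.** Section 2.4 reports delays in 49% of eribulin patients in the earlier phase III trial. Both arms receive eribulin, so this is shared background. If 49% of Arm B slip one week per interval, and 49%, 59%, 69% or 79% of Arm A do, type I error is 0.104, 0.114, 0.124 or 0.137.

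**The case against.** The strongest reply is that the rule is deliberate, stated three times without contradiction and identical in both arms. Harm needs a difference in delays, and the documents do not show one. Several provisions work against a difference: eribulin may continue when only pembrolizumab is held, both arms share the same laboratory criteria for treating on later Day 1 visits (Section 5.2.2), eribulin stops if a delay exceeds 3 weeks, off-treatment scans run on calendar weeks, and deaths are dated exactly.

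Most of this is right, and it limits the size. Scenarios with no delay in Arm B are upper bounds, because every Arm B patient receives eribulin. The effect can also run the other way: Arm B later makes the test conservative, and Arm A later raises power. But these provisions reduce the difference between arms without removing it, and an unknown direction is no protection. Either direction distorts the comparison, and exact progression times cannot be recovered once scans have moved.

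One related conflict should be kept apart. Section 5.7 gives 6- then 9-week scans after unconfirmed progression, where Section 11.1 gives 9 then 12. That arises only after the first RECIST progression, so it mainly affects PFS per irRECIST.

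**Conclusion.** The concern holds, on its stated condition. The scan rule lets dosing delay set event and censoring dates for the primary endpoint, and the analysis plan has nothing to detect or correct an imbalance. Equal delays leave the test sound. With a realistic shared background and a modest excess in Arm A, type I error would be about 0.11 to 0.15 against 0.10, and about 0.165 at a full extra week. With the excess in Arm B, type I error falls to about 0.055–0.083 and power to 77–80%. Values near 0.19 need delays in Arm A only. All of these rest on assumed delay patterns; the documents establish neither size nor direction. The gap in Section 5.8 adds to the problem: the assumed Arm A median of 7.1 months is about week 31 (7.1 × 52.18/12), inside the weeks for which that section gives no interval.

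**What to change.** Anchor tumour assessments in both arms to weeks from randomization, at the calendar's existing intervals (9 weeks in the first year, then 12). They should not move for a dose delay, for stopping one or both drugs, or for coming off treatment before progression. Exempt scans from the delay sentences in Sections 5.1 and 6 and in footnote f. Reconcile the intervals in Sections 5.7 and 5.8 and footnote i with the calendar. In Simulation 2, a common schedule without delay gives type I error 0.102 and power 83.6%.

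A by-arm summary of actual scan times and an interval-censored sensitivity analysis of PFS would show any imbalance, including in patients already scanned under the present rule.

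The cost is small. The change is to protocol wording, with no new type of scan and no change to any dosing rule. When dosing is delayed, some scans, and the cell-free DNA samples tied to restaging visits (Sections 9.1 and 9.7.5), may not fall on a Day 1 visit.
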